### **Background, Rationale and Context**

Ventral hernia repair (VHR) is a common procedure performed by general surgeons with an estimated 400,000 per year performed in the United States [1]. Based on available literature, experts strongly recommend mesh reinforcement for all elective VHR of hernias at least 2cm in diameter with no contamination. There is currently no conclusive recommendation for mesh reinforcement in emergent VHR, VH < 2cm, or in the setting of contamination [2]. There are numerous types of mesh available, including biologic and synthetic. Because synthetic mesh has been associated with a host of complications including infection, adhesions, bowel obstruction, and enterocutaneous fistula, biologic meshes were developed and are widely available in various types. They provide an acellular collagen matrix on which the host tissue can regenerate [3]. Biologic meshes are generally significantly more expensive than their synthetic counterparts [4,5] although long-term cost analysis has suggested that biologic mesh may be more cost-effective due to the long-term complication rates for synthetic mesh [5]. Few studies have compared the various types of biologic mesh [6]. In this study, we aim to compare two different types of biologic mesh in VHR: Fortiva and Strattice to determine the difference in rates of hernia recurrence and mesh related complications. Fortiva is an FDA cleared (510(k)) biologic mesh that is “substantially equivalent” to Strattice mesh but at a reduced cost making the mesh more cost efficient. The risks associated with this study are expected to be the same as those associated with a VHR utilizing Strattice mesh.

### **Goal**

The goal of this research study is to show that Fortiva porcine dermis biologic mesh is equivalent to Strattice biologic mesh with respect to hernia recurrence rates and mesh related complication rates. Fortiva is an FDA cleared (510(k)) hernia mesh that is substantially equivalent to Strattice but at a reduced cost. The goal is to show similar equivalent outcomes to justify the use of Fortiva.

### **Objectives**

**Primary Objective:** To determine the hernia recurrence rates for RTI Surgical biologic mesh (Fortiva) compared to Strattice

**Hypothesis:** Fortiva mesh will have equivalent rates of hernia recurrence compared to Strattice

**Secondary Objective(s):** To determine the mesh related complications for RTI Surgical biologic mesh (Fortiva) compared to Strattice

**Hypothesis:** Fortiva mesh will have equivalent rates of mesh related complications compared to Strattice

### **Methods and Measures**

#### **Design**

This study will be a prospective, matched study of patients using Fortiva biologic mesh to determine the rates of hernia recurrence and mesh related complication compared to a retrospective cohort of patients who received Strattice mesh. The indication CLASP surgeons use for biologic mesh use is in contaminated/dirty cases; surgeons are sometimes unable to determine this until they are in the OR. To account for the nature of biologic mesh use in

ventral hernia repair, patients whom an attending surgeon uses Fortiva mesh in the OR when it was not otherwise planned (i.e. the surgeon changed the plan intraoperatively) will be approached in the postoperative space (i.e. follow-up clinic visits or phone calls) to be consented for inclusion in the study. In the event a subject cannot be reached in clinic prior to the end of their standard of care follow-up, a full waiver of consent will be requested to capture all patients and not unnecessarily skew the results. The rates of hernia recurrence and mesh related complications will be compared to determine equivalence. Patients who meet the inclusion and exclusion criteria will be prospectively enrolled to receive a Ventral Hernia Repair (VHR) using Fortiva biologic mesh and will be compared to a retrospective cohort of patients with a VHR that utilized Strattice mesh. All procedures and clinical care have already occurred for the participants who received a VHR with Strattice mesh. Participants will be propensity matched in a 1:3 (Fortiva : Strattice) fashion based on age, sex, and hernia defect size to control for confounding variables.

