### **Subjects selection criteria**

Patients who meet the following criteria will be included in the study.

- **Inclusion Criteria**

- Aged at least 18 years
  - Ventral Hernia requiring surgical repair

- **Exclusion Criteria**

- Pregnant women
  - Sensitivity to Polysorbate 20

- **Sample Size**

This study will have a sample n=200 (n=50 Fortiva, n=150 Strattice). All participants may not be eligible for the study, so this study may consent up to 100 prospective participants to achieve the 50-participant sample size. This study will serve as a pilot study to compare rates of hernia recurrence and mesh related complications between Fortiva and Strattice. Our group has published research in press showing a 4% hernia recurrence rate for Strattice mesh. Based on an alpha level of 0.05 and a beta of 0.80 and a non-inferior limit of 2% the sample size per group would be 1188. Based on these numbers we would like to do a matched pilot study with a more feasible sample size of 200 participants (n=50 Fortiva(retrospective and prospective), n=150 Strattice(retrospective)).

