#### **Informed Consent**

Signed informed consent will be obtained from each subject in the prospective group. Informed consent will be obtained by a member of the research team (PI, Co-I, fellow, resident, research manager, or research associate) in the clinic prior to the date of surgery. Informed consent may be obtained on the day of surgery, if the patient has been contacted previously prior to the day of surgery, via telephone, and has stated an interest in participating in the research study.

A full waiver of consent/assent and a waiver HIPAA authorization will be requested for patients in the retrospective group as their procedures and outcomes have already happened and reporting on the procedures and outcomes will not adversely affect the patient's care. Access to age in years and

office/clinic notes will be requested. Access to patient name, phone number and MRN will be the only identifying information requested. The study material is identifiable; however, study data will be linked by an identifier assigned to each participant and the identifier will be the only information maintained in the study data. The standard operating procedure for our group is to keep all study data in a locked suite, locked file cabinet, or electronically via password protection on a secure computer, on a secure network. Identifiers will be kept as part of the participants' medical record indefinitely. Access to this information is requested to identify patients who have already undergone VHR with Strattec mesh and would be of the retrospective cohort.

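### Patients switched to Fortiva in theatre may be asked for consent after their outcome is known, and the plan has no rule for those who are reached and decline

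*Combined protocol and SAP*

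**What the plan says.** The Design section explains that surgeons sometimes learn only in the operating room that a case is contaminated, which is their indication for biologic mesh. Patients switched to Fortiva at that point "will be approached in the postoperative space (i.e. follow-up clinic visits or phone calls) to be consented for inclusion in the study". No latest time for this approach is set other than the end of standard follow-up. Interventions and Interactions lists contacts at 2 weeks, 6 months and 1, 2 and 3 years.

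The waiver for these patients is conditional: "In the event a subject cannot be reached in clinic prior to the end of their standard of care follow-up, a full waiver" is to be requested. Its stated purpose is "to capture all patients and not unnecessarily skew the results".

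The Informed Consent section treats the comparator differently: "A full waiver of consent/assent and a waiver HIPAA authorization will be requested for patients in the retrospective group", a group it describes as patients repaired with Strattice. For the other group it says: "Signed informed consent will be obtained from each subject in the prospective group". It places that consent "in the clinic prior to the date of surgery", or on the day of surgery after an earlier telephone contact. It provides no postoperative route.

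Under Sample Size, "this study may consent up to 100 prospective participants to achieve the 50-participant sample size". The same paragraph labels the 50 Fortiva patients as both retrospective and prospective.

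**The concern.** The outcomes are recurrence and mesh-related complications. A switched patient approached at a late visit may already have had one of them, and both the patient and the team may know it. Willingness to join could then depend on the result being measured. A planned Fortiva patient can also decline, but before or on the day of surgery, when there is no outcome to react to. A Strattice patient cannot decline at all.

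Selection of this kind would act on one side of the comparison. Propensity matching on age, sex and defect size does not address it, nor does the general regression in the Analytical Plan, because the decliners' outcomes would be absent. No count of decliners is planned, so a reader of the results could not tell whether it had happened. This is a pilot, so a distorted Fortiva rate could also carry into the planning of a larger study.

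**Working it through.** **The plan's own figure.** With 4% recurrence in both arms, a 2-point limit, one-sided alpha 0.05 and 80% power (reading the stated beta of 0.80 as power):

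n = 2 × 0.04 × 0.96 × (1.645 + 0.842)² / 0.02² = 1187.05, rounded up to 1188 per group.

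This matches the protocol and is not in dispute. It supplies the 4% rate and the 2-point limit used below.

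**Inputs**
- From Sample Size: p = 4%; 50 Fortiva and 150 Strattice patients.
- Assumed, because the documents give no figure: s, the share of Fortiva patients switched and approached after surgery, 30-50%; d1 and d0, the refusal rates with and without recurrence, between 10% and 50%.

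**Formula.** Observed rate = p(1 − s·d1) / [p(1 − s·d1) + (1 − p)(1 − s·d0)]

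| s | d1 | d0 | Calculation | Observed |
|---|---|---|---|---|
| 0.3 | 0.3 | 0.1 | 0.0364 / (0.0364 + 0.9312) | 3.76% |
| 0.5 | 0.5 | 0.1 | 0.0300 / (0.0300 + 0.9120) | 3.18% |
| 0.3 | 0.1 | 0.3 | 0.0388 / (0.0388 + 0.8736) | 4.25% |
| 0.5 | 0.1 | 0.3 | 0.0380 / (0.0380 + 0.8160) | 4.45% |
| 0.5 | 0.1 | 0.1 | equal refusal | 4.00% |

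The shift is therefore about −0.8 to +0.5 points, and zero when refusal is unrelated to outcome.

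**Wider assumptions.** If half the arm is switched and 50% of patients without recurrence refuse against 10% with it, the observed rate is 0.038 / (0.038 + 0.720) = 5.01%. If the whole arm were switched, refusal of 50% against 10% in either direction gives 2.26% to 6.98%.

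**Comparison with chance.** The expected number of recurrences is 50 × 0.04 = 2. The standard error of the Fortiva rate is √(0.04 × 0.96 / 50) = 2.8 points. The largest central shift, 0.8 points, is about 0.3 standard errors.

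**Timing.** The formula applies d1 to every recurrence among switched patients. That is right only if the recurrence came before the approach. A patient approached at 2 weeks cannot be influenced by a later recurrence, so these figures are near a worst case for the refusal rates assumed. Early wound complications are more likely to precede the approach. The plan gives no rate for them, so their shift is not computed here. The shift in points equals p(1 − p)·s·(d0 − d1) / [1 − s(p·d1 + (1 − p)·d0)], so at the same refusal rates an event more common than 4% moves further, until it approaches half of patients.

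**The case against.** The strongest reply is that the investigators saw the risk and provided for it: the waiver for unreached patients exists so as not to skew the results. What remains is a narrower gap, patients who are reached and decline. Nothing in the text says that their data are discarded; that is inferred from the consent requirement. Nothing suggests that refusal depends on outcome. The label on the Fortiva sample may mean that some Fortiva patients also enter under waiver, although Informed Consent describes the retrospective group as Strattice patients. All of this stands, and it limits the point without removing it. The waiver as written does not reach its own stated aim.

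A reader might infer that the bias is as large as the whole non-inferiority limit, since one refusal after recurrence turns 2/50 (4.0%) into 1/49 (2.04%). The arithmetic is correct, but it is not the expected effect. The assumptions above imply 2 × s × d1 = 2 × 0.3 × 0.3 = 0.18 to 2 × 0.5 × 0.5 = 0.50 such refusals when refusal is higher after recurrence. A decliner might also be replaced, because enrolment aims at 50. The protocol itself says that the 2-point limit needs 1188 per group and calls this study a pilot.

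A reader might also infer that the rule favours Fortiva. The documents do not support a direction: patients who are well may be the ones who see no reason to take part. Nor is the bias beyond remedy, since a log of decliners allows bounds.

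**Conclusion.** The concern holds as a gap in the consent rule. Following the Design section lets outcome-dependent refusal enter the Fortiva arm, with no matching opportunity among the Strattice patients described under Informed Consent. On the central assumptions a true 4% recurrence is observed as about 3.2-4.5%, of unknown sign and well inside sampling error at 50 patients. The range rests on an assumed switched share and assumed refusal rates, on decliners being lost, and on recurrence preceding the approach. It matters because it is systematic, because it would be invisible without a log, and because early wound complications are more exposed than recurrence. It should be corrected, but it does not by itself invalidate the pilot.

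Separately, the consent passages do not agree. Design allows consent after surgery and a waiver for some switched patients; Informed Consent requires signed consent before or on the day of surgery from every prospective subject.

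**What to change.** 1. **Consent before surgery.** Ask scheduled patients in whom biologic mesh is considered possible to consent to data collection if Fortiva is used. Check the ceiling: if all 50 came by this route, 100 consents suffice only if at least half receive Fortiva, and the protocol's stated reason for the allowance is ineligibility, not non-use of the mesh. Cost: an IRB amendment, extra consent conversations and possibly a higher ceiling.
2. **One outcome-independent rule for switched patients without prior consent.** Either approach all of them at the earliest contact, before discharge or by the 2-week visit, or use a records-only waiver if the IRB agrees, settled before any approach. The waiver is debatable. Its present justification, that procedures and outcomes have already happened, does not clearly fit patients still under follow-up, and records-only data would omit the study telephone contacts, so ascertainment would differ within the arm.
3. **Log every Fortiva implant.** Report the numbers consented before surgery, consented after, waived and declined. With x events in n analysed patients and k decliners, give the bounds x/(n + k) and (x + k)/(n + k). An analysis excluding postoperative consents may be added, but it also changes case mix, because switched patients are those whose contamination was found in theatre. With 30-50% switched it leaves 25-35 patients and 1.0-1.4 expected recurrences. Cost: a short log and a few lines in the analysis plan.
4. **Reconcile the text.** Align Design with Informed Consent on the timing and route of consent, state how patients who decline are handled, and say which Fortiva patients the label retrospective covers and under what consent they enter.

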### **Interventions and Interactions**

This study will involve surgical ventral hernia repair utilizing a biologic hernia mesh (Fortiva). Fortiva mesh may be used by a CLASP surgeon in ventral hernia repair in patients even if they choose not to participate in the research study.

- This study will involve the implantation of RTI Surgical Fortiva biologic mesh in the reconstruction of the abdominal wall. Mesh size, position, location and procedure will be determined and performed by an attending surgeon from Carolinas Laparoscopic & Advanced Surgery Program (CLASP).
- Study participants will be asked to follow up for at least 36 months.
  - Follow up will include participants being seen back in clinic as part of our standard of care after a ventral hernia repair or contacted via telephone at 2-weeks, 6-months, 1-year, 2-year, 3-year to evaluate the participants progress and recovery using the Fortiva mesh

Data elements to be collected are listed below:

Protocol version: 5

- Age
- Sex
- Race
- Body mass index (BMI)
- Comorbidities
  - Asthma
  - Cirrhosis
  - Congestive heart failure (CHF)
  - COPD
  - Coronary Artery Disease
  - Current Steroid Use
  - Current Anticoagulant Use
  - Diabetes history
  - Hemoglobin A1c
  - End Stage renal Disease
  - History of Cancer
  - Hypertension
  - Obstructive Sleep Apnea
  - Peripheral Vascular Disease
  - Smoking history
  - Current smoking status
  - Stroke History
  - Transplant patient
- Hernia defect size
- At the time of Surgery
  - Fistula present(y/n)
  - Mesh infection(y/n)
- Mesh size
- Mesh type
- Mesh location (preperitoneal, intraperitoneal, inlay/bridging, retrorectus, onlay)
- Number of hernia failures
- Number of hernia procedures
- Type of hernia procedures (emergent vs elective)
- Dates of Surgery
- Use of botox (y/n)
- American Society of Anesthesiologist (ASA) Classification
- Operative findings
  - Complete Fascial closure(y/n)
  - Enterotomy
- Use of component separation techniques (external oblique release or transversus abdominus release) to enable closure
- Length of Operation
- Recurrence(y/n)
- TAPP block
- Mesh resection
- Concomitant procedures
- Concurrent panniculectomy
- Mesh fixation (sutures/glue/none)
- Delayed primary skin closure(y/n)

- Wound complications(y/n)
  - Wound cellulitis
  - Wound infection
  - Surgical site infection (SSI)
  - Superficial wound breakdown
  - Intra-abdominal abscess
  - Seroma requiring intervention
  - Mesh infection
- Length of Stay
- Mortality

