### **Analytical Plan**

Results will be analyzed initially using descriptive statistics. Comparison between groups will be done using chi square tests for proportions, and t-tests or ANOVA procedures for continuous variables. Regression analysis will be performed to identify independent outcome predictors. Other inferential statistical analysis will be conducted as appropriate.

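### The propensity match omits contamination, the protocol's own indication for biologic mesh, and no adjusted mesh contrast is committed to; imbalance is possible but not shown

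*Combined protocol and SAP*

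**What the plan says.** - **Comparator and match (Design).** Fortiva patients are compared with a retrospective, non-randomised Strattice cohort. Patients are "propensity matched in a 1:3 (Fortiva : Strattice) fashion based on age, sex, and hernia defect size to control for confounding variables".
- **Indication (Design).** "The indication CLASP surgeons use for biologic mesh use is in contaminated/dirty cases"; the text adds that "surgeons are sometimes unable to determine this until they are in the OR".
- **Eligibility (Subjects selection criteria).** Adults with a ventral hernia that needs surgical repair are eligible. The only exclusions are pregnancy and polysorbate 20 sensitivity. Contamination is not mentioned.
- **Data elements (Interventions and Interactions).** Wound class is not listed. Related items are: fistula and mesh infection at surgery, enterotomy among the operative findings, and "Concomitant procedures". Other baseline factors are collected but not matched on, among them BMI, diabetes history, smoking, emergent versus elective procedure and earlier hernia failures.
- **Analysis (Analytical Plan).** Descriptive statistics come first. Then, "Comparison between groups will be done using chi square tests for proportions", with t-tests or ANOVA for continuous variables. "Regression analysis will be performed to identify independent outcome predictors". A closing sentence allows further inferential analysis where appropriate.

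**The concern.** Without randomisation, the match is the only control of confounding that the plan commits to. It leaves out the one clinical factor that the protocol itself names as driving the use of biologic mesh. Contamination could plausibly affect recurrence, and could affect the wound and mesh infection items among the complications directly.

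The Goal section wants similar outcomes to support using the cheaper mesh. If contamination is neither balanced nor tabulated by arm, a reader cannot tell whether a similar or a different rate reflects the mesh or the case mix. The error could go either way: it could hide a worse mesh or penalise an equal one.

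**Working it through.** **1. The plan's own figure.** The only calculation in the plan is 1188 per group (Sample Size). With 4% in both groups, a 2-point limit, one-sided alpha 0.05 and power 0.80:

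n = 2 × 0.04 × 0.96 × (1.645 + 0.842)² / 0.02² = 1187.05, rounded up to 1188.

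It reproduces. It concerns sampling error only and says nothing about confounding, for which the plan gives no figure.

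**2. Could an outcome model repair the match?** Inputs from Sample Size: 50 Fortiva, 150 Strattice, 4% recurrence.

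- Expected recurrences: 50 × 0.04 = 2 and 150 × 0.04 = 6, so 8 in total.
- With four covariates that is 8/4 = 2 events per covariate, before counting a mesh term.

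For recurrence, adjustment therefore belongs mainly in the propensity model, where the limiting number is the 50 Fortiva patients: 50/4 = 12.5 per term with four terms.

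The plan gives no rate for mesh complications. If it were 10% to 30% (assumed), 200 patients would yield 20 to 60 events, or 5 to 15 per covariate with four. The few-events limit is therefore shown for recurrence only.

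**3. Size of a possible false difference.** The documents give neither contamination prevalences nor a risk ratio, so both are assumptions. Let qF and qS be the contaminated proportions in the Fortiva and Strattice arms, and RR the recurrence risk ratio, contaminated versus clean. Assume no true mesh effect and 4% overall in Strattice:

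- clean-case risk r = 0.04 / [(1 − qS) + qS × RR]
- Fortiva risk = r × [(1 − qF) + qF × RR]
- false difference = Fortiva risk − 0.04

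For example, with qF = 0.9, qS = 0.7 and RR = 3: r = 0.04/2.4 = 0.01667; Fortiva risk = 0.01667 × 2.8 = 0.0467; difference +0.67 points.

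| qF vs qS | RR 1 | RR 1.5 | RR 2 | RR 3 |
|---|---|---|---|---|
| equal | 0 | 0 | 0 | 0 |
| 90% vs 70% | 0 | +0.30 | +0.47 | +0.67 |
| 70% vs 90% | 0 | −0.28 | −0.42 | −0.57 |
| 80% vs 50% | 0 | +0.48 | +0.80 | +1.20 |
| 40% vs 80% | 0 | −0.57 | −0.89 | −1.23 |

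The 90% and 70% rows sit closest to the stated indication, under which most cases in both arms should be contaminated. The last two rows fit it less well and show how the answer moves with the assumptions. No row is an upper bound.

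**4. Against the pilot's precision.** 95% half-width = 1.96 × √[0.04 × 0.96 × (1/50 + 1/150)] = 1.96 × 0.032 = 6.27 points, treating the arms as independent. So 0.67/6.27 is about 11% of it, and 1.23/6.27 about 20%.

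**5. Would a balance table show it?** Standardised difference for 90% vs 70% = 0.20 / √[(0.09 + 0.21)/2] = 0.52. That is plain if contamination is abstracted and invisible if it is not.

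**The case against.** The strongest reply is that both arms received biologic mesh from surgeons who reserve it for contaminated cases, so practice already restricts both cohorts. Descriptive statistics come first and could show differences on the listed proxies. The regression could include mesh type. Three propensity terms for 50 patients is defensible parsimony, and this is a declared pilot whose sampling error exceeds the illustrated bias.

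Much of this stands. The shared indication partly aligns the arms, and nothing in the documents shows imbalance. But the indication describes practice and is not an eligibility rule, and the plan does not commit to checking the overlap. Allowing a regression is not committing to an adjusted mesh contrast. A fourth term is still modest for 50 patients.

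Stronger readings that a reader might infer, and that the documents do not support:

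- *The comparison is biased.* Only the gap in control is shown.
- *Contamination goes unrecorded.* Proxies are listed, and the data collection form named in the Appendix is not reproduced, so a wound-class field cannot be excluded.
- *No multivariable analysis is planned.* One is planned; what it estimates is left open.
- *The bias would matter greatly at 1188 per group.* The protocol sets that size aside in favour of the pilot and proposes no such study.
- *Fortiva patients are all later than Strattice patients.* Sample Size describes the Fortiva group as both retrospective and prospective, so surgery dates may overlap.

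**Conclusion.** The concern holds as a gap in design and specification. Followed as written, the plan leaves a confounder that it names itself outside the match and commits to no contrast that would adjust for it.

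The size is uncertain and probably modest in this pilot: 0 to about 0.7 points in either direction under the assumptions closest to the stated indication, against a half-width of 6.3 points. This rests on assumed prevalences and risk ratios, on 4% recurrence in Strattice, and on no true mesh effect. It is zero if the arms are equally contaminated or if contamination does not affect recurrence. The change is worth making because it is cheap and because, without it, the overlap between arms may never be seen.

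**What to change.** 1. Add contamination to age, sex and defect size in the propensity model, giving four terms.
2. Define it the same way in both arms: wound class from the operative note or, if that is unavailable, a composite of the listed at-surgery proxies (fistula, mesh infection at surgery, enterotomy, contaminating concomitant procedure). The postoperative mesh infection outcome must not enter the composite.
3. Fix the definition before the matched outcome comparison is run. The group already has a Strattice recurrence rate in press, so that is the realistic cut-off.
4. Report standardised differences by arm for contamination and the other collected baseline factors.
5. State in the Analytical Plan that the mesh effect is estimated in the matched sample.

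**Cost.** Contamination must be abstracted for the whole Strattice candidate pool, whose size is not given, and not only for the 150 selected. The composite also needs a judgement on which concomitant procedures contaminate. The waiver request in Informed Consent names clinic notes and may need to name operative notes, although the listed operative items seem to need them already.

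Some Fortiva patients may get fewer than three matches, and the estimate must then allow for unequal set sizes. If the Strattice arm fell to 100, the half-width would be 1.96 × √[0.0384 × (1/50 + 1/100)] = 6.65 points, up from 6.27.
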